**Inclusion/Exclusion Criteria (recorded by [name] Team in REDCap):**

1. 13-35 years old
2. Acute ACL injury in the past 6 months who have had ACL reconstruction in the past month or have a planned ACL reconstruction
3. No previous knee injury or surgery to either knee
4. Body mass index (BMI) > 35 kg/m^2
5. No concomitant PCL injury
6. Cartilage procedure that include extended weightbearing restrictions and/or changes to cartilage structure (e.g. OATS)
7. Current pregnancy or plans to become pregnant during the study duration (self-report)
  - a. If a female participant becomes pregnant they are no longer eligible for the MRI portion of the study. They will complete other study components as able.

**Study Design**

1. Prospective, parallel clinical trial
2. Participants will be tested at enrollment (2 weeks after ACLR or when 50% weightbearing is allowed) and again after completing the study intervention at 3 months and 6 months post ACLR.

**Sample Size and Randomization**

1. N=34 (17 in squat biofeedback group and 17 in control group)
  - a. Target equal number of women and men

**Recruitment & Patient Tracking**

-[name] Team will keep a potential patient tracking spreadsheet on Box to track pre-op and early post-operative eligible patients

-Potential participants will be discussed at bi-weekly meetings

-When patient is ready to enroll:

1. [name] will email consent form and study info to patient/parents
2. [name] will assign subject ID, enter into REDCap, complete REDCap screening form, and assign to group (post-ACLR)
3. If pre-intervention PT is needed, [name] will schedule first treatment session
4. [name] will inform RJ of when patient is to be in clinic for RJ to meet patient and schedule testing sessions.

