**Informed Consent:**

Methods:

1. Participation in the study (and providing copy of informed consent form) must occur at least 1 day after participant (and guardian) is approached about the study
2. Informed consent will be completed before or at the participant's first PT treatment session or at 2-week testing in the CMOVA Lab (if previous PT completed elsewhere).
3. Informed consent will be completed by [name] (if completed first PT treatment session) or RJ/[name].

4. There is a single consent form for both adults and minors (<19 years old) with a guardian. Minors must also be provided the youth information sheet. Consents forms will be on Box. Make sure to use a version with the current time stamp in the lower right corner of each page.
5. Participants (or guardian) also need to fill out the narrative consent form to indicate who they would like the testing results to be shared with (i.e. surgeon, athletic trainer, etc.)
6. Must be obtained in a private room that is well lit with little to no distraction.
7. Participant is instructed on the consent form and provided time to read the consent form. At any time they are encouraged to ask questions and clarify any issues. 15 minutes is allotted. More time will be given if needed.
8. To ensure understanding, the participant (and guardian) will be asked if they understand the consent form and if they have any specific questions. Best practice is to ask the participant to provide a brief overview of the testing methods and timing of the follow-up testing.
9. A copy of the fully signed consent form and the narrative consent must be provided to the participant/guardian.

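### The listed enrolment order allows the group to be assigned before consent is signed and places it before baseline testing, and no random sequence or concealment is described

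*Combined protocol and SAP*

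**What the plan says.** Recruitment & Patient Tracking gives a numbered list for a patient who is ready to enrol:

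1. A staff member "will email consent form and study info to patient/parents".
2. One role assigns the subject ID, makes the REDCap entry, and must "complete REDCap screening form, and assign to group (post-ACLR").
3. If pre-intervention PT is needed, a staff member "will schedule first treatment session".
4. The tester is told when the patient will be in clinic, "for RJ to meet patient and schedule testing sessions".

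On the signature, the Informed Consent section says: "Informed consent will be completed before or at the participant's first PT treatment session or at 2-week testing in the CMOVA Lab". The last option is for those whose earlier PT took place elsewhere.

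On baseline, Study Design says: "Participants will be tested at enrollment (2 weeks after ACLR or when 50% weightbearing is allowed").

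The section headed Sample Size and Randomization gives the total of 34, the 17/17 split and one further line: "Target equal number of women and men". It does not mention a sequence, a list holder, blocks or concealment.

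**The concern.** Allocation protects a comparison only if nobody who decides on entry, including the patient, can know or influence the arm before entry is settled. Here the screening form and the group assignment sit in one step under one role, and the signature may come later.

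Two things could follow. Staff who know or can foresee the arm could press harder for some patients than for others. Patients or guardians who learn the arm before signing could decline because of it, and would then be lost after allocation.

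Masking offers no second line of defence for participants or therapists. One arm watches a feedback screen and the other does not, and the two arms are cued differently. The analysis cannot repair the damage either. The ANCOVA on squat mechanics adjusts for baseline knee flexion moment impulse, not for unmeasured prognosis. Cartilage T2 change, which the sample size text labels primary, is compared by a t-test with no covariates.

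**Working it through.** The point rests on the order of events, so the main check sets the sections side by side.

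**Consent against assignment.** The Informed Consent section allows three routes.

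| Signature given | Position relative to step 2 |
|---|---|
| Before the first PT session | Not settled; may fall before or after assignment |
| At the first PT session | After assignment in the listed order, since that session is booked in step 3 |
| At the 2-week lab test | After assignment in the listed order, since testing is booked following step 4 |

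Two of the three routes put assignment before the signature if the list is followed, and the third leaves it open.

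**Baseline against assignment.** Testing sessions are arranged only once the tester is informed in step 4. On every route, the listed order places assignment before baseline testing.

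**Is the arm needed that early?** The Bodyweight Squat Protocol starts 2 weeks after surgery, with its first sessions in weeks 3-4. Where weightbearing is restricted, the modifications table delays baseline testing and the start of the protocol together. The Cuing section ties the group-specific cues to the squat protocol period, and step 3 itself calls the earlier PT pre-intervention. Nothing in the schedule requires the arm before baseline testing is done.

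**Is a sequence or concealment described elsewhere?** Study Design calls the trial prospective and parallel. The random number generator under Biofeedback Details picks the feedback condition for a set, not the arm. The items varied at random by the therapist are timing, location and arm position. The Statistical Analysis Plan is silent on allocation. The method is not described anywhere.

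**Illustration of what a bias would do.** The bias sizes are assumptions; the documents give none.

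Inputs from the sample size text: T2 difference 2.9 ms, SD 2.7 ms, 15 per group, stated power 81.0%. Alpha is 0.05. The test is taken as two-sided, which the plan states for other endpoints but does not repeat for T2.

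Formula: noncentrality = difference / (SD × √(2/n)), with 2n − 2 degrees of freedom.

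- Plan's figure: 2.9 / (2.7 × √(2/15)) = 2.9 / 0.986 = 2.94 on 28 degrees of freedom. Power is 81.0%, so the stated value reproduces.
- No true effect, but a selection-driven difference of b SD: noncentrality = b / √(2/n). The probability of p < 0.05 is then:

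| Assumed b (SD) | In ms (b × 2.7) | Noncentrality, n = 15 | False-positive rate, 15 per arm | False-positive rate, 17 per arm |
|---|---|---|---|---|
| 0.1 | 0.27 | 0.27 | 5.8% | 5.9% |
| 0.2 | 0.54 | 0.55 | 8.3% | 8.7% |
| 0.3 | 0.81 | 0.82 | 12.5% | 13.6% |
| 0.5 | 1.35 | 1.37 | 26.2% | 29.3% |

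The rate is higher with 17 per arm because a fixed bias is detected more readily as n grows. Enrolling more patients would not help.

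**The case against.** The strongest defence is that the documents are incomplete on this point, not demonstrably wrong. Several firmer readings are tempting, and the text does not support them.

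- **That assignment always precedes consent.** The consent sentence includes the option of signing before the first PT session. The only timing attached to assignment is that it follows surgery. Because patients may be tracked before surgery, that qualifier may be there to hold assignment back from the rest of step 2. Some participants may well sign first.
- **That allocation is not concealed, or not random.** A section heading names randomization, and assignment is listed alongside REDCap entry. A concealed list may exist. The documents show only that none is described.
- **That baseline is measured with the arm known.** Step 4 tells the tester when the patient will be in clinic; it does not say the arm is disclosed. The squat test is also standardised by metronome and scripted cues.
- **That one person both judges eligibility and assigns.** The role in step 2 completes the screening form, but the criteria are recorded by a team and candidates are discussed at meetings. Names are masked, so overlap between the assigner and the person taking consent cannot be checked.

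All four cautions stand. They do not remove the narrower point: the listed order permits assignment before the signature and places it before baseline, and no safeguard is described that would make this harmless.

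**Conclusion.** The concern holds in limited form. One role completes screening and assigns the arm in the same step. The written order allows this before signed consent and places it before baseline testing. The plan describes no sequence generation, list holder or concealment. In a trial that cannot mask participants or therapists, this leaves room for selective enrolment and for arm-driven refusals after allocation.

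The size of any bias cannot be estimated from the documents. The false-positive rates above are conditional on assumed biases and are not evidence that bias exists. The conclusion on timing assumes that the numbered list is meant as a sequence. No stated sample size or power figure changes. The absence of a described method would by itself be a request for detail. The order of steps is a stated workflow, can be corrected at almost no cost, and cannot be repaired by analysis once patients are enrolled.

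**What to change.** In Recruitment & Patient Tracking, take group assignment out of step 2 and make it a separate, later step that is allowed only when three conditions are recorded in REDCap: consent signed, eligibility confirmed, baseline testing completed. Pre-intervention PT can still be booked beforehand, because it does not depend on the arm.

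Release the arm from a random list generated in advance and held in the REDCap system already in use, so that screening staff can neither see nor choose the next allocation. Under Sample Size and Randomization, state how the list is generated, who prepares and holds it, and who can view it. If such a list already exists, describe it and still reorder the steps.

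Stratifying by sex is optional and not part of this fix; the stated sex target can be read as a recruitment target and does not require it.

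The cost is a short wording change and a one-time REDCap setup, with no extra visits or staff. The one drawback is that the arm becomes known only after baseline, so the first squat session has to be scheduled a little more tightly.

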**Informed Consent:**

Methods:

1. Participation in the study (and providing copy of informed consent form) must occur at least 1 day after participant (and guardian) is approached about the study
2. Informed consent will be completed before or at the participant's first PT treatment session or at 2-week testing in the CMOVA Lab (if previous PT completed elsewhere).
3. Informed consent will be completed by [name] (if completed first PT treatment session) or RJ/[name].

4. There is a single consent form for both adults and minors (<19 years old) with a guardian. Minors must also be provided the youth information sheet. Consents forms will be on Box. Make sure to use a version with the current time stamp in the lower right corner of each page.
5. Participants (or guardian) also need to fill out the narrative consent form to indicate who they would like the testing results to be shared with (i.e. surgeon, athletic trainer, etc.)
6. Must be obtained in a private room that is well lit with little to no distraction.
7. Participant is instructed on the consent form and provided time to read the consent form. At any time they are encouraged to ask questions and clarify any issues. 15 minutes is allotted. More time will be given if needed.
8. To ensure understanding, the participant (and guardian) will be asked if they understand the consent form and if they have any specific questions. Best practice is to ask the participant to provide a brief overview of the testing methods and timing of the follow-up testing.
9. A copy of the fully signed consent form and the narrative consent must be provided to the participant/guardian.

**Lab Testing Order:**

1. Warm-up as needed (5 min; treadmill, stationary bike or overground (e.g. squats/lunges))
2. Height & Weight
3. ROM
4. Effusion
5. Volitional Isometric & Isokinetic Quadriceps Strength (Biodek)
6. Biomechanics
7. Surveys

**Height & Weight (all testing sessions):**

Equipment: Stadiometer  
 Methods: 1. Shoes off; record in kilograms and inches

**Knee Active Range of Motion (all testing sessions):**

Equipment: High-Low Table  
 Goniometer  
 Methods:

1. Patient in supine (bolster/towel roll under ankle for extension)
2. Proximal arm along lateral midline of femur in line with greater trochanter
3. Distal arm along lateral midline of fibula in line with lateral malleolus
4. Flexion: Patient maximally bends their knee actively (without self-assist or assist from research staff).
5. Extension: Patient contracts quad and maximally extends his/her knee actively. Hyperextension recorded as e.g. "hyper 5." Lacking full knee extension recorded as e.g. "lack 3."

**Knee Effusion Testing (all testing sessions):**

Equipment: High-Low Table  
 Methods: Sturgill et al. 2009 JOSPT

**Volitional Isometric & Isokinetic Quadriceps Strength Testing (Biologix) (3, 6 months):**

Equipment: Biologix (C-MOVA)

Set-Up:

- a. Use participant weight measured in lab
- b. Before participant is ready to test (while performing other testing)
  - i. Power on machine: turn on black button then computer
  - ii. Open Biologix
  - iii. Go to patient → if new patient go to add patient → enter patient information (Last name, first name, gender, involved limb, weight (kg), enter RTS under ID #)
  - iv. If returning patient, click open and select patient → select the last testing session → select repeat and same protocol will automatically be applied
  - v. Click save
- a. Click protocol → click Linked → Select RTS Testing or RTS Testing plus 180 per sec depending on time point.
  - 1. ISOM: UNI: AWAY: TEST: 90, 90, 90 (RTS Isometric: KNEE: EXT/FLX **(3, 6 months)**)
  - 2. ISOK: UNI: CON/CON: TEST: 60/60 (RTS Isokinetic): KNEE: EXT/FLX **(3, 6 months)**
  - 3. ISOK: UNI: CON/CON: TEST: 180/180 (RTS Isokinetic): KNEE: EXT/FLX **(6 months)**
  - 4. ISOM: UNI: AWAY: TEST: 90, 90, 90 (RTS Isometric: KNEE: EXT/FLX **(3, 6 months)**)
  - 5. ISOK: UNI: CON/CON: TEST: 60/60 (RTS Isokinetic): KNEE: EXT/FLX **(3, 6 months)**
  - 6. ISOK: UNI: CON/CON: TEST: 180/180 (RTS Isokinetic): KNEE: EXT/FLX **(6 months)**
- c. Set up chair positioning (will test uninvolved limb first) (if 6-month testing then set up according to 3-month testing position)
  - i. Seat A/P forward/backward position
  - ii. Seat height
  - iii. Seat depth
  - iv. Attachment Arm length
  - v. Dynamometer distance left/right
  - vi. Set-up guidelines:
    - a. Secure thigh, chest, and waist straps
    - b. Top of dynamometer cuff just proximal to talocrural joint (2 finger widths above medial malleolus)
    - c. Knee joint center should be in line with arm of rotation of dynamometer
- e. After subject is set-up, complete testing:
  - i. Select side

- ii. Set away limit
- iii. Set toward limit
- iv. For calibrate position: use level to calibrate arm at 90 degrees
- v. For limb weight put limb to end extension ROM and lock in that position and ask subject to relax
- vi. Select continue
- vii. Select start
- viii. Isometric: Begin trial reps
  - 1. Have subject cross arms over chest when ready to contract
  - 2. Practice trials at 50%, 75%, and 100% of maximum effort completed to assure no pain or discomfort present.
    - a. Note: If pain exceeded 2/10, actions taken to change the tibiofemoral joint angle or add towel for cushion between dynamometer and shank
- ix. Select close once practice reps are completed
- x. Instructions to participant:
  - a. For this test, you will kick out as hard and as fast as you can.
  - b. Cross your arms across chest to help stabilize yourself, but do not grab the shoulder straps.
  - c. On my signal to begin, kick out as hard and as fast as you can and continue that until I tell you to stop.
  - d. 3 – 2 – 1 – Go - KICK KICK KICK
  - e. One minute between reps; 3 recorded trials (up to 5 max)
- xi. Isokinetic (60°/sec and 180°/sec): Explain to the participant as soon as we hit the start button the practice trials will begin and the real trials will start once they pull back and hold.
  - a. Have subject cross arms over chest when ready to contract
  - b. Practice trials at 100% of maximum effort completed to assure no pain or discomfort present
- xii. Once the practice trials are complete the participant must continue small movements to prevent Biodex from prematurely starting trials. When the participant is ready they are instructed to hold back to full flexion as it was measured with the ROM and hold it there to tell the system that the participant is ready to begin the trial and it will start automatically. If it doesn't start automatically help the participant hold the attachment back until the system honks and begins.
- xiii. Instructions to subject:
  - a. For this test, you will kick out as hard and as fast as you can.
  - b. Cross your arms across chest to help stabilize yourself
  - c. On my signal to begin, kick out as hard and as fast as you can and then pull back as hard and as fast as you can. Move from 90 degrees until your knee is straight and all the way back each time. You will complete 5 reps each direction.
  - d. 3 – 2 – 1 – KICK KICK KICK, PULL PULL PULL
  - e. 1 recorded trial
- xiv. Record peak torques on data collection form as you go

- f. Change to other side
  - vi. Select “no” to auto set range of motion
    - i. Select set range of motion
    - vii. Select clear limits
    - viii. Repeat steps i-xii
- g. Repetitions:
  1. Isometric at 90° - Minimum on each side: 3. Maximum on each side: 5. Test unininvolved limb first.
  2. Isokinetic at 60°/sec - Minimum on each side: 1 set of 5 alternating repetitions. Maximum on each side: 3 sets of 5 alternating repetitions. Test unininvolved limb first.
  3. Isokinetic at 180°/sec - Minimum on each side: 1 set of 10 alternating repetitions. Maximum on each side: 3 sets of 10 alternating repetitions. Test unininvolved limb first.
- h. Pain is only to increase by 2/10 from pain in standing; either 1) modify foot position or 2) modify testing angle or 3) attempt patellar taping or 4) omit the testing (if unable to test involved knee, still test unininvolved knee)

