## Statistical Analysis Plan

### **Data analysis plan:**

A p-value less than 0.05 will be considered statistically significant unless otherwise specified.

To determine the efficacy of the visual biofeedback program, analyses of covariance (ANCOVA) will be used at 3 and 6 months after ACLR to test differences in the interlimb ratio (ILR = injured limb / uninjured limb) of the knee flexion moment impulse during squatting, after adjusting for baseline knee flexion moment impulse. An ANCOVA will also be used to test differences in the ILR of the vertical ground reaction force impulse.

Independent t-tests will be used to test the percent change in cartilage T2 relaxation time in the injured knee from 2 weeks to 6 months after ACLR between groups, quadriceps strength, and gait biomechanics. For quadriceps strength, limb symmetry indexes will be computed (LSI = injured limb / uninjured limb x 100%).

If assumptions for any of these tests are violated, a nonparametric test will be conducted.

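### Pain rules allow a changed test angle with no matched uninjured-limb value, so an affected participant's strength LSI could divide torques from two angles

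*Combined protocol and SAP*

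**What the plan says.** All of the testing text is in the section Volitional Isometric & Isokinetic Quadriceps Strength Testing.

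- **Order and angle.** The set-up step reads "Set up chair positioning (will test uninvolved limb first) (if 6-month testing then set up according to 3-month testing position". The repetitions list gives "Isometric at 90° - Minimum on each side: 3. Maximum on each side: 5. Test unininvolved limb first". After the first limb, the tester changes side and repeats the numbered steps, including the practice trials.
- **Pain during isometric practice trials.** "If pain exceeded 2/10, actions taken to change the tibiofemoral joint angle or add towel for cushion between dynamometer and shank".
- **Pain rule at the end of the section.** "Pain is only to increase by 2/10 from pain in standing", followed by four options: "either 1) modify foot position or 2) modify testing angle or 3) attempt patellar taping or 4) omit the testing". The only instruction here about the other limb is that the uninvolved knee is still tested when the involved knee cannot be.
- **Recording.** The tester writes peak torques on a data collection form. The text does not ask for the angle used.
- **Analysis.** Under Data analysis plan, "limb symmetry indexes will be computed (LSI = injured limb / uninjured limb x 100" per cent. No test mode (isometric, 60°/sec or 180°/sec) is named, and nothing requires the two torques to come from the same angle.

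**The concern.** Limb order and the pain rules interact. The injured knee is the one more likely to be painful, and it is tested second. By the time an angle change is considered, the uninjured limb has already been recorded at 90 degrees. The steps then end without going back.

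Isometric torque depends on joint angle. A ratio of injured torque at one angle to uninjured torque at another therefore reflects both the strength deficit and the angle difference, and the two cannot be separated afterwards. Without a matched trial from that session, the value cannot be repaired at analysis.

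Strength LSI has its own power calculation under Sample size analysis (66.0% against 90.0%, SD 21.1%, 15 per group). With about 15 analysed per arm, a few distorted values count.

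**Working it through.** **1. The plan's own figure.** Inputs from Sample size analysis: difference 90.0 − 66.0 = 24.0 points, SD 21.1, 15 per group; alpha 0.05. Noncentrality = 24.0 / (21.1 × √(2/15)) = 3.11 on 28 degrees of freedom. Two-sided t-test power is 85.2%; one-sided it is 91.8%. The stated 91.8% for a two-sided test is therefore reproduced only as one-sided. That is a separate matter. The baseline used below is 85.2%.

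**2. Does the text prevent a mismatch?**

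- Carrying the 3-month chair position to 6 months standardises across visits, not between limbs. The settings listed (seat position, height and depth, arm length, dynamometer distance) do not include the test angle.
- Repeating the steps on the second limb also repeats the practice-trial note that permits an angle change. It does not return to the first limb.
- The instruction for an untestable involved knee covers omission, not a test at another angle.
- The LSI formula takes whatever two torques are recorded.

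So nothing prevents a mismatch, though nothing directs one.

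**3. Effect on one participant.** Let r = torque at the changed angle / torque at 90 degrees. The documents give no torque-angle relation, so r from 0.8 to 1.2 is an assumption. Recorded LSI = true LSI × r.

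| r | true 66% reads | true 90% reads |
|---|---|---|
| 0.8 | 52.8% | 72.0% |
| 0.9 | 59.4% | 81.0% |
| 1.1 | 72.6% | 99.0% |
| 1.2 | 79.2% | 108.0% |

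At a true 66%, the error is 6.6 to 13.2 points.

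**4. Effect on the comparison.** Let a share f of an arm be affected (assumption: 10%, 20%, 30%). The arm mean becomes m = μ(1 − f + fr), and its variance (1 − f + fr²)(SD² + μ²) − m². Two-sided power at 15 per group:

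| r | f | both arms: difference, power | control arm only: difference, power |
|---|---|---|---|
| 0.8 | 10% | 23.5, 83.3% | 25.3, 88.7% |
| 0.8 | 20% | 23.0, 81.6% | 26.6, 91.7% |
| 0.8 | 30% | 22.6, 80.3% | 28.0, 94.1% |
| 1.2 | 10% | 24.5, 83.4% | 22.7, 79.6% |
| 1.2 | 20% | 25.0, 82.2% | 21.4, 73.3% |
| 1.2 | 30% | 25.4, 81.4% | 20.0, 66.5% |

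For 20% of the control arm and none of the other, the shift is 0.20 × 6.6 = 1.3 to 0.20 × 13.2 = 2.6 points.

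**5. The two pain triggers (separate).** Let standing pain be s out of 10. The practice-trial note acts above 2. The end-of-section rule acts above s + 2. They coincide only at s = 0. At s = 2, the first acts at 3/10 and the second not until pain is above 4/10.

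**The case against.** **The angle change is optional.** The practice-trial note offers a towel as an alternative, and the later rule offers foot position, taping or omission. A reader might infer that a painful injured knee is always moved to another angle and that the LSI will then be wrong. The text does not say so. It permits the change and is silent on matching. This objection stands, so the claim is only that the LSI could mix angles.

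**The test mode is not named.** The isokinetic trials run from 90 degrees to a straight knee, so there is no single angle to mismatch. This stands too: the point in its main form is conditional on an isometric LSI.

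**The form may have an angle field.** It is not in the documents, so its absence cannot be asserted. But an angle field alone would identify an unmatched pair without supplying the missing denominator.

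**The size is modest.** A shift of 1.3 to 2.6 points is about 5-11% of 24 points, or 0.06-0.13 SD, and rests on a one-sided split. With both arms affected alike, power stays at about 80% or more. A reader might infer that the comparison is biased because pain differs by arm. Nothing in the documents shows that: both arms do the same sets and repetitions, and although feedback and cueing differ, no pain data are given. T2 relaxation time, not LSI, is the outcome labelled primary.

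**The pain triggers could operate together**, whichever is met first. That is possible, but the text does not say it, and the discrepancy is not needed for the LSI point.

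**Conclusion.** The gap is real but conditional. A permitted angle change, combined with a fixed limb order and an LSI without a matched-angle condition, can give an invalid ratio that cannot be recovered after the session. It applies only to participants for whom the angle option is used. It concerns angle if the LSI is isometric, and range of motion if it is isokinetic.

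For an affected participant, the error at a true LSI of 66% is 7 to 13 points, on the assumption that torque changes by 10-20%. At trial level, equal use in both arms mainly adds noise: power is about 80-83% against 85.2%, with the expected difference moving by less than 1.5 points. Bias of more consequence needs unequal use. The lowest power shown, 66.5%, needs 30% of controls and no intervention participants affected, all with r = 1.2. The documents support neither that pattern nor any particular direction of error, so this is not evidence that the strength comparison is underpowered or biased as planned.

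The differing pain triggers are a separate inconsistency. This review takes no view on which should apply.

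**What to change.** 1. In the SAP, name the test mode (and time point) used for the strength LSI.
2. Record the test angle for each limb at every session.
3. Add to the testing section: when the angle is changed for the injured limb, repeat the uninjured-limb isometric trials at that angle after adequate rest.
4. Add to the SAP: LSI is computed only from torques at the same angle; unmatched pairs are treated as missing, and their number is reported by arm. If isokinetic torque is used, state the equivalent condition for range of motion.
5. Reconcile the practice-trial note and the end-of-section pain rule so that one trigger is stated.

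Cost: in affected sessions, a few extra minutes, another change of side, and 3 to 5 further maximal trials with the one-minute rests already specified. Fatigue in the uninjured limb could lower the denominator, so the repeats should be identified in the data. Treating unmatched pairs as missing loses some values, and those losses are related to pain. No change to treatment is involved, but the rule must be in place before a session is run.
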